4.9.2 SUBGROUP ANALYSES

No correction for multiple testing in subgroup analysis will be undertaken and multiplicity-unadjusted p-values will be reported, although the number of declared subgroup analyses will be specified in all publications.

The following subgroup analyses will be carried out for the primary outcome:

- Type of fibrosing ILD (IPF vs other)
- Severity of ILD (FVC<50% vs ≥50%predicted)

The effect of this factor will be assessed by adding an interaction term to the main model.

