2.4 RANDOMISATION AND BLINDING

Following baseline assessment participants are randomly allocated (1:1) to receive AOT or sham AOT (air) delivered by the Inogen One G3 HF POC. A computer generated, permuted block randomisation is used with stratification for (i) desaturation during 6MWT (<80% vs ≥80%) and (ii) site of recruitment. A remote, web-based, computer-generated randomisation procedure is used (provided by NHMRC Clinical Trials Centre).

Participants, clinicians and researchers will be blinded to group allocation. The Inogen One G3 HF POCs for AOT and air groups will be identical in appearance, display, weight and operation, with the only difference being the gas delivered. POCs were coded by the distributor, BOC, who have no involvement in trial conduct. All participants are advised against measuring oxygen saturation at home during the duration of the trial, as this does not represent usual clinical practice in any of the centres and may unblind the participants.

At the conclusion of the trial, participants are asked two questions to evaluate the success of blinding:

- Which treatment do you think you were receiving, oxygen or air?
- Did you have a pulse oximeter at home over the last 6 months? If yes, how did you use it?

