4.7 PATIENT CHARACTERISTICS AND BASELINE COMPARISONS

In order to assess balance, description of the specified baseline characteristics will be presented for the Oxygen and Air groups (Table 1). Discrete variables will be summarized as frequencies and percentages. Unless otherwise indicated in the tables percentages will be calculated according to the number of patients for whom data are available. Continuous variables will be summarized by use of either mean and standard deviation or median and interquartile range. Durations and time intervals will be summarized by medians, IQRs, and ranges.

Baseline measures for patients will be presented by group for the following variables:

age, gender, body mass index, type of fibrosing ILD, respiratory function (FEV1, FVC and TLCO, absolute and %predicted), 6-minute walk distance (metres), resting SpO₂, nadir SpO₂ on 6MWT (%), % of waking hours with SpO₂ ≤ 88% during daily life, physical activity (average steps/day), Dyspnoea-12, KBILD, Hospital Anxiety and Depression Scale.

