4.9.1 MAIN ANALYSIS

The primary analysis will use linear mixed models, with site as a random effect. We will compare change from baseline at 3 and 6 months between groups, with the baseline measurement included in the model as a covariate. The treatment effect will be presented as the mean difference between groups with the corresponding 95% confidence interval. Desaturation during 6MWT, although a stratifying factor in the design, will be modelled as a fixed effect.

The assumption of homogeneity of variance will be examined for each outcome by plotting residuals from the model against fitted values. Where right skewness results in heterogeneity of variance, a log transformation will be applied.

Missing data are anticipated for the primary outcome. The primary outcome is assumed to be missing-at-random (MAR), i.e. it is assumed that the probability of 3 month steps/day data being missing may depend on the values of the observed data, but not on the values of the missing data. Important explanatory and auxiliary variables such as age, type of ILD, respiratory function and extent of exertional desaturation are being collected and will be examined to assess the plausibility of the MAR assumption.

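### The severity subgroup tests effect modification only through a cut of FVC at 50% predicted, and 6MWT desaturation is adjusted for but not tested as an effect modifier

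*SAP*

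**What the plan says.** SAP section 4.9.2 declares two subgroup analyses for the primary outcome: "Type of fibrosing ILD (IPF vs other" and "Severity of ILD (FVC<50% vs ≥50%predicted", each with the closing bracket omitted here. The method is given in one sentence: "The effect of this factor will be assessed by adding an interaction term to the main model". That sentence is in the singular, but I read it as covering both subgroups.

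Section 4.7 lists among the baseline variables "respiratory function (FEV1, FVC and TLCO, absolute and %predicted", so the continuous FVC value is available. No analysis of the treatment effect over continuous FVC is planned. The SAP gives no mean, SD or expected share below 50% predicted, and sections 2.2.1 and 2.2.2 set no FVC limit for entry.

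Section 2.4 describes randomisation with "stratification for (i) desaturation during 6MWT (<80% vs ≥80%) and (ii) site of recruitment". Section 4.9.1 then states: "Desaturation during 6MWT, although a stratifying factor in the design, will be modelled as a fixed effect". The same section names the extent of exertional desaturation among the variables used to judge whether missing at random is plausible. No treatment-by-desaturation term appears in the SAP.

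**The concern.** A subgroup question about severity asks whether the benefit changes as lung function falls. A single cut treats everyone on the same side of 50% as alike, so differences within each side add nothing to the test. The further the cut lies in the tail, the fewer participants inform one side. A null interaction could then reflect the coarse test rather than the absence of effect modification.

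The second part concerns which modifier is examined. Exertional desaturation is an entry criterion, a stratification factor and a model covariate. Whether participants who desaturate more deeply respond differently is a natural question in an oxygen trial. If the interaction is not declared in advance, any later answer will be post hoc.

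Section 4.1 gives subgroup analyses a supporting role. What is at stake is how informative that supporting evidence is, not the primary result.

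**Working it through.** **Inputs from the SAP.** Section 2.5: 220 participants (110 per group), target 599 steps per day, SD 1582, 80% power, two-sided 5%. Section 2.4: 1:1 allocation. The share below 50% predicted (p) and the share below 80% saturation are not given, so both are assumptions shown as ranges.

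**1. The plan's own figure.** n per group = 2 × (1.960 + 0.842)² × 1582² / 599² = 109.5, rounded up to 110, or 220 in total. Power with 110 per group is 0.80. The stated sample size reproduces, so its inputs can be carried forward.

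**2. Information kept by the cut.** For a normal modifier with a linear interaction, the information kept is the squared correlation between the modifier and its two-level version: φ(z_p)² / [p(1 − p)]. At p = 0.5 this is 0.3989² / 0.25 = 0.637. At p = 0.2 it is 0.2800² / 0.16 = 0.490.

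**3. Precision of the two-level interaction.** SE = 2 × 1582 / √[220 p(1 − p)]. The difference in effect detectable at 80% power is 2.802 × SE.

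| Share below cut | n of 220 | Information lost | SE | Detectable difference (steps) | Power for a 599-step difference |
|---|---|---|---|---|---|
| 50% | 110 | 36% | 427 | 1195 | 29% |
| 40% | 88 | 38% | 435 | 1220 | 28% |
| 30% | 66 | 42% | 465 | 1304 | 25% |
| 25% | 55 | 46% | 493 | 1380 | 23% |
| 20% | 44 | 51% | 533 | 1494 | 20% |
| 15% | 33 | 57% | 597 | 1674 | 17% |
| 10% | 22 | 66% | 711 | 1992 | 13% |
| 5% | 11 | 78% | 979 | 2742 | 9% |

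The loss reaches one half at p = 0.209.

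**4. Where p might lie.** Assumed normal FVC distributions, none from the SAP: mean 65, SD 20 gives 23% below and 48% lost; mean 65, SD 15 gives 16% and 56%; mean 70, SD 18 gives 13% and 60%; mean 75, SD 18 gives 8% and 69%. The 36% minimum belongs to the normal shape. For a flat distribution the share kept is 3p(1 − p), so a cut at the median would lose 1 − 0.75 = 25%.

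**5. Gain from continuous FVC.** Assume for illustration a modification of 400 steps per SD of FVC. The continuous test has SE = 2 × 1582 / √220 = 213, so 400 / 213.3 = 1.875 and power is Φ(1.875 − 1.960) = 47%. For the cut, the expected difference is 400 × φ(z_p) / [p(1 − p)]. At p = 0.10 this is 400 × 1.95 = 780, and 780 / 711 gives about 20% power. At p = 0.15 and 0.25 the power is 23% and 28%.

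**6. Desaturation interaction.** With an assumed 30% to 50% of participants below 80%, the formula in step 3 gives a detectable difference of 1304 to 1195 steps, which is 2.2 to 2.0 times 599. Power for a 599-step difference is 25% to 29%.

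**7. Effect of baseline adjustment.** Steps 3, 5 and 6 use SD 1582 unreduced, whereas section 4.9.1 adjusts for baseline. If 1582 is a between-patient SD and the baseline-to-follow-up correlation is 0.7 (assumed), the residual SD is multiplied by √(1 − 0.49) = 0.714. Then 1992 becomes about 1420, and 1304 to 1195 becomes about 931 to 853. The percentages lost in step 2 do not change, because the SD cancels.

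**The case against.** The strongest reply is that the plan is orderly as it stands. The subgroups are few and prespecified, tested by interaction and given a supplementary role, and the SAP promises that publications will state how many were declared. Stratifying by a factor does not oblige a plan to make it a subgroup, and declining a further unadjusted test is defensible. A reason for the 50% cut may stand in the protocol, which is not shown. If the effect does step at 50%, the cut is the efficient test and the linear term is not. The proposed tests also lack power. All of this stands, and it keeps the point a minor one. It does not remove the case for using a variable already collected in a more informative way under a plausible smooth relation.

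Three stronger readings are tempting but not supported:

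- A reader might infer that the cut discards half or more of the information. That needs about 21% or fewer below 50%, and the SAP gives no FVC distribution. With 25% below, the loss is 46%. Nor do the eligibility criteria establish that only a handful will be below the cut.
- A reader might infer that desaturation is ignored. It is adjusted for as a fixed effect and considered when judging missingness. Only its interaction with treatment is absent.
- A reader might infer that desaturation is the only factor balanced by design. Section 2.4 also stratifies by site.

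**Conclusion.** The point holds as a low-cost improvement. Under a roughly normal FVC and a roughly linear modification, the 50% cut loses at least about 36% of the information on the severity interaction. For shares of 50% down to 5% below the cut, the loss runs from 36% to 78%. It would be nil under a true step at 50%.

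The absolute detectable differences depend on SD 1582 without baseline adjustment and are probably pessimistic. The comparison of 47% with 20% to 28% power rests on an assumed 400 steps per SD and only illustrates the direction of the gain.

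The missing desaturation interaction is a secondary matter. Its value lies in an estimate declared in advance, not in a decisive test. Neither part touches the primary analysis or its conclusion.

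**What to change.** Two changes of wording in SAP section 4.9.2, made before unblinding:

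1. Make the severity test the interaction of treatment with FVC % predicted as a continuous variable, with its main effect in the model. Report the change in treatment effect per unit of FVC with a 95% confidence interval. Keep the 50% split to display effects on either side, so that readers have a rough check on linearity.
2. Declare a third subgroup analysis: treatment by desaturation stratum (<80% vs ≥80%), reported as an estimate with a 95% confidence interval, and count it in the number of declared subgroups.

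If unblinding has already taken place, both analyses should be labelled post hoc.

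No new data are needed. The cost is a linearity assumption for FVC and one more unadjusted interaction test with low power (step 6 of the working).

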4.9.3 OTHER SENSITIVITY ANALYSES

Not planned.

4.10 ANALYSIS OF SECONDARY OUTCOMES

Changes in secondary outcomes listed in 2.2.4 will be compared between groups using linear mixed models, using the same random and fixed factors as for the primary outcome, including the baseline measure of the outcome as a covariate.

- 4.10.1 Change in functional exercise capacity assessed by 6-minute walk distance
- 4.10.2 Change in health-related quality of life evaluated using the St George's Respiratory Questionnaire
- 4.10.3 Change in health-related quality of life evaluated using the K-BILD Questionnaire
- 4.10.4 Change in dyspnea measured using the Dyspnea-12 questionnaire
- 4.10.5 Changes in fatigue evaluated by the Fatigue Severity Scale
- 4.10.6 Change in anxiety and depression measured by the Hospital Anxiety and Depression Scale
- 4.10.7 Change in time spent in moderate to vigorous physical activity
- 4.10.8 Change in sedentary time

4.11 ANALYSIS OF SAFETY OUTCOMES

Adverse events are defined according to the Good Clinical Practice guidelines including treatment emergent adverse events (TEAE's), which are undesirable events not present prior to medical treatment, or that worsen either in intensity or frequency following treatment. AEs of specific interest are defined according to the criteria used in the LOTT trial (6):

- worsening of lung function (absolute FVC decline >5% predicted over the 6-month trial) (7)
- development of resting hypoxaemia (arterial oxygen pressure ≤ 55 mmHg at rest on room air, or 56–59 mm Hg with evidence of right heart failure)
- exacerbation of fILD
- hospitalization
- death
- bruising or infection at blood draw site
- fainting related to blood draw
- fainting, dizziness, chest pain, ataxic gait, lower limb pain or mental confusion related to 6-minute walk test
- Adverse events related to POC use:
 - burns (from smoking whilst using a POC, using the POC around an open flame or equipment that sparks)
 - nosebleed or dry nose
 - musculoskeletal injury from tripping on a POC

For each category, we will report both the total number of events and the proportion of participants with at least one event. The proportion of participants with at least one event will be compared between randomised groups using generalised linear mixed models (GLMMs) with a binary outcome and the same random effects as for the main analysis. The number of exacerbations and hospitalisations will be compared between groups using GLMMs with a Poisson or Negative Binomial model for the counts. The number of adverse events related to POC use will be compared between groups using similar GLMMs.

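### SAP 4.11 leaves the desaturation stratum out of the binary safety models and gives the event-count models neither covariates nor a time-at-risk term.

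*SAP*

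**What the plan says.** Randomisation uses "stratification for (i) desaturation during 6MWT (<80% vs ≥80%) and (ii) site of recruitment" (SAP 2.4). The main model follows this design: "The primary analysis will use linear mixed models, with site as a random effect", and "Desaturation during 6MWT, although a stratifying factor in the design, will be modelled as a fixed effect" (SAP 4.9.1). For the secondary outcomes, SAP 4.10 carries over both parts, "using the same random and fixed factors as for the primary outcome".

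SAP 4.11 is worded differently. The proportion of participants with at least one event is compared by a generalised linear mixed model with "a binary outcome and the same random effects as for the main analysis". Fixed factors are not mentioned. For counts, "The number of exacerbations and hospitalisations will be compared between groups using GLMMs with a Poisson or Negative Binomial model for the counts". Counts of POC-related events get models described only as similar. Neither count sentence names a random effect, a fixed effect, an offset or a rule for shortened follow-up.

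One safety category is tied to a single late measurement: "worsening of lung function (absolute FVC decline >5% predicted over the 6-month trial". SAP 4.11 gives no denominator for participants without that measurement.

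**The concern.** There are two separate gaps.

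**Stratum.** Read literally, 4.11 brings over site and stops. The desaturation stratum is a design factor and plausibly prognostic for events such as hospitalisation and death. It would then be in the efficacy models but not in the safety models, and no reason is given.

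**Follow-up time.** A Poisson or negative binomial model without an offset compares mean counts per person, not rates. A participant followed for one month with no event then contributes the same zero as one followed for six. The plan expects incomplete follow-up: SAP 2.5 randomises 260 so that 220 complete. If one arm loses more people early, its raw counts look lower for that reason alone, and in a harm comparison that error is in the reassuring direction.

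**Working it through.** **Plan's own figures (SAP 2.5).** Difference 599, SD 1582, two-sided 5%, 80% power: n per arm = 2 × (1.96 + 0.842)² × 1582² / 599², which rounds up to 110, or 220 in total. This agrees with the plan and is not affected by the present point. Planned non-completion is 1 − 220/260 = 15.4%. SAP 4.11 states no safety figure to reproduce.

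**Scope of the carry-over wording.** SAP 4.9.1 has one random effect (site) and makes desaturation fixed. SAP 4.10 carries random and fixed factors. SAP 4.11 carries random effects for the binary models and names none for the counts. The stratum is therefore outside the wording of every safety model, and site is outside the wording of the count models.

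**Size of the count effect.** Assume no true treatment effect, constant event rates, and exits spread evenly over 6 months. Mean exposure in an arm with exit share d is then 1 − d/2, and the expected count ratio is the ratio of exposures. The splits by arm are assumptions; the last three rows hold the overall share at about 15.4%.

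| Exits, arm A vs arm B | Exposure A, B | Null count ratio B/A |
|---|---|---|
| 10% vs 20% | 0.950, 0.900 | 0.947 |
| 15.4% vs 15.4% | 0.923, 0.923 | 1.00 |
| 10% vs 20.8% | 0.950, 0.896 | 0.943 |
| 5% vs 25.8% | 0.975, 0.871 | 0.893 |

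For the type I error, take 130 per arm and 0.3 to 0.5 events per person per 6 months (assumed), with expected counts A = 130 × rate × exposure and B likewise, shift = ln(B/A) and SE = √(1/A + 1/B). For 10% vs 20.8% at rate 0.5: A = 61.75, B = 58.24, shift = −0.0585, SE = 0.183, rejection rate 6.2%. At rate 0.3 it is 5.7%. For 5% vs 25.8% it is 7.7% to 9.5%. With equal exits it is 5.0%.

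**Size of the stratum effect.** Assume two equal strata, 15% control risk in the lower-risk stratum, a treatment odds ratio of 2.0 within each stratum, and 130 per arm.

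- Stratum odds ratio 3: control risks 0.150 and 0.346 (mean 0.248); treated risks 0.261 and 0.514 (mean 0.388). Odds ratio without the stratum = (0.388/0.612)/(0.248/0.752) = 1.92. SE of the log odds ratio 0.271 without the stratum and 0.281 with it; z = 2.40 and 2.47.
- Stratum odds ratio 5: mean risks 0.309 and 0.450. Odds ratio without the stratum = 1.82. SE 0.259 and 0.280; z = 2.32 and 2.48.
- With milder assumptions (stratum odds ratio 2 to 3, 20% base risk), 2.0 becomes 1.96 to 1.91.
- A treatment odds ratio of 1.0 stays 1.0 throughout.

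**The case against.** The strongest reply is that this is silence rather than error, with small consequences. Naming a Poisson or negative binomial model does not rule out an offset. The count comparison is distorted under the null only if exits differ by arm. The SAP gives no reason to expect that: it states only an overall loss, and the sham device is identical and blinded. Stopping the POC or starting LTOT is not itself an exit, because SAP 4.6 and 4.8 keep those participants in the analysis. Some categories, such as burns or fainting at a blood draw, may be too sparse for a stratum term.

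Most of this stands as a limit on size. It does not answer the point that an analyst following 4.11 as written would compare raw counts over unequal follow-up and leave out a design factor that 4.10 retains.

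Three stronger readings are tempting and are not supported:

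- **Missing 6-month FVC counted as no decline.** A reader might infer this from the intention-to-treat wording. The SAP nowhere says so, and SAP 4.1 bases the main analysis on available outcome data, which allows those participants to be left out of this proportion. What is open is the denominator.
- **FVC decline should become a composite with death.** That would change a defined safety category, and death is already a category of its own.
- **Omitting the stratum costs precision.** The standard errors above are smaller without it. The shift in the odds ratio is the difference between a marginal and a conditional odds ratio, with slightly lower power.

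**Conclusion.** The point holds as a gap in model specification with modest effect. SAP 4.11 omits the desaturation stratum from the binary safety models, and its count models have no stated factors and no time at risk.

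The missing time-at-risk term matters more. It moves a null count ratio to about 0.94 to 0.95 at roughly 10% against 20% exits, to 0.89 at a more extreme split, and not at all if exits are equal. These values rest on assumed exit splits, even timing of exits and constant rates. The missing stratum matters less: under assumed stratum odds ratios of 3 to 5, an odds ratio of 2.0 becomes 1.92 to 1.82, z falls from about 2.5 to 2.4 or 2.3, and a null effect is untouched. The primary result and the sample size are not affected.

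**What to change.** In SAP 4.11:

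1. State that all safety models, binary and count, use the same random and fixed factors as the main model (site random, desaturation stratum fixed), and that the stratum is dropped only where events are too sparse to fit it.
2. Add log(days at risk) as an offset in all count models, including those for POC-related events, and define days at risk.
3. At most, add one sentence saying that the FVC proportion uses participants with a 6-month FVC, with deaths shown alongside.

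The cost is wording. The stratum is already held from randomisation, and days at risk needs only start and exit dates. There are two downsides. Sparse categories may not support the stratum term, so some models will differ from others. The offset assumes roughly constant rates and exit unrelated to event risk, which is open to doubt if sicker participants leave early, so follow-up time by arm should be reported next to the rate comparison.

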4.12 ANALYSIS OF TERTIARY OUTCOMES

- 4.12.1 Portable oxygen concentrator usage, reported as total hours at 3 and 6 months, and mean hours per day. Differences between randomized groups will be compared.
- 4.12.2 Reason for cessation of therapy where relevant (patient request, commencement of LTOT, other) will be reported as number and percent of randomized group.
- 4.12.3 Oxygen saturation in daily life at 3 and 6 months, measured using a Nonin 3150 Wrist Oximeter during waking hours for 2 consecutive days. Reported as % of monitored time with $SpO_2 \leq 88\%$ during daily life and compared between randomised groups.

These outcomes will be analysed using similar models to those used for the primary and secondary outcomes, depending on whether the data are continuous, binary or counts.

- 4.12.4 We will conduct an exploratory analysis to investigate the impact of portable concentrator usage (mean hours per day) on the primary outcome of mean steps/day using linear mixed models, with POC usage modelled as a random effect.

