2.2.3 PRIMARY OUTCOME

- Change from baseline in physical activity at 3 months, measured by the number of steps per day. Steps per day is measured using the StepWatch activity monitor (SAM) (Modus Health, Washington DC, USA). The SAM is worn on the ankle continuously for 7 days (except for bathing) at baseline, 3 months and 6 months. Days with < 8 hours recording or < 200 steps will be excluded. The mean number of steps per day will be calculated using the mean for all included days.

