2.2.6 TERTIARY OUTCOMES

- Use of oxygen therapy, downloaded from POC flash memory, measured in hours at 3 and 6 months
- Reason for cessation of therapy where relevant (patient request, commencement of LTOT, other).
- Oxygen saturation in daily life, measured using a Nonin 3150 Wrist Oximeter during waking hours for 2 consecutive days at 3 and 6 months.

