2.3 INTERVENTION

For the oxygen group, ambulatory oxygen therapy will be delivered using the Inogen One G3 HF POC. Ambulatory air will be delivered using the Inogen One G3 HF POC that has been modified by the manufacturer to deliver only air. The POCs are identical in appearance.

All participants are informed that the aim of using a POC is to assist them to be more active, with fewer symptoms. They are encouraged to use the POC at all times when they are moving about, including walking at home or in the community, during exercise or during other activities. The POC should not be used when sitting still or sleeping. Written and verbal education are provided. Participants are encouraged to use their allocated POC during physical activity for the 6-month study period. The Inogen One G3 HF POC is used at its maximum flow setting of 5 for both groups.

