2.5 SAMPLE SIZE

A total of 220 participants (110 per group) would provide 80% power to detect, at the two-sided 5% level, a clinically important difference between groups in the primary outcome of 599 steps per day (3). This assumes an SD of 1582 steps, based on physical activity data previously collected at our centre in 52 patients with fILD

(4). Previous experience suggests that 5% of participants could start LTOT (and cease POC use) over 6 months. We therefore intended to randomise 260 participants to ensure that 220 participants completed the study.

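### Exploratory analysis 4.12.4 cannot show an impact of POC hours on steps/day, because both arms are told to use the POC when moving; it should be reported as an association, by arm

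*SAP*

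**What the plan says.** SAP section 4.12.4 sets an exploratory aim, to "investigate the impact of portable concentrator usage (mean hours per day) on the primary outcome of mean steps/day", and gives the method as "using linear mixed models, with POC usage modelled as a random effect". It names no treatment arm term, no usage-by-arm contrast and no caution about how usage arises.

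Section 2.3 gives the same instruction to both arms: "They are encouraged to use the POC at all times when they are moving about, including walking at home or in the community". It adds: "The POC should not be used when sitting still or sleeping". The air device looks identical and delivers only air.

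The two measurements come from different instruments. Usage is described in section 2.2.6 as "Use of oxygen therapy, downloaded from POC flash memory, measured in hours at 3 and 6 months". Steps come from an ankle monitor (section 2.2.3): "The SAM is worn on the ankle continuously for 7 days (except for bathing) at baseline, 3 months and 6 months".

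Section 2.5 expects that "5% of participants could start LTOT (and cease POC use) over 6 months".

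**The concern.** The exposure in 4.12.4 is partly produced by the outcome. A participant who follows section 2.3 logs POC hours by moving about, and the step counter records the same movement. Walking can raise usage as readily as usage can raise walking, and usage is observed only after randomisation. Disease progression may add to the association, since someone who starts LTOT stops using the POC and may also be walking less.

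What is at stake is interpretation. Suppose the primary comparison is null and this analysis shows that heavier users walked more. Under the word *impact*, that invites a reading as dose-response, or as poor adherence explaining the null result. The same pattern would be expected in the air arm, where hours of use deliver no oxygen, and 4.12.4 does not plan to look there separately.

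**Working it through.** **1. The plan's own figure.** The SAP gives no number for 4.12.4. Its sample size (section 2.5) supplies the only documented inputs: difference 599, SD 1582, two-sided 5%, 80% power.

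n per arm = 2 × (1.960 + 0.842)² × (1582/599)² = 2 × 7.85 × 6.975 ≈ 109.5, rounded up to 110, or 220 in total. Power at 110 per arm is 80.2%. The stated size reproduces.

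**2. The mechanism.** Write POC hours = adherence × moving hours + use at rest, with moving hours = steps ÷ steps per moving hour. Assume 1500 steps per moving hour, constant adherence of 0.5 and no use at rest. One extra POC hour then goes with 1500/0.5 = 3000 extra steps, with no oxygen effect at all. Variable adherence, noise and baseline adjustment flatten this slope.

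**3. Simulation with zero oxygen effect.** 400 trials per scenario; 3-month steps regressed on POC hours, arm and baseline steps by ordinary least squares.
- From the SAP: N = 220 and SD 1582, used here as the SD of steps at each visit.
- Assumed: mean 3500 steps/day, 1500 steps per moving hour, lognormal noise 0.25, median adherence 50%, no use at rest, and hours and steps reflecting the same period.

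Average pooled slope, steps/day per POC hour:

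| Baseline to 3-month correlation | Adherence logit SD 0.5 | 1 | 2 |
|---|---|---|---|
| 0.5 | +1462 | +980 | +590 |
| 0.7 | +1189 | +735 | +434 |
| 0.85 | +788 | +451 | +253 |

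The slope was positive with p<0.05 in 98.8% of runs in the last cell and 100% elsewhere. The air arm alone gave +254 to +1467 (significant in 86% to 100%); at correlation 0.7 and logit SD 1 it gave +747 against +735 pooled. Baseline adjustment reduces the slope but does not remove it.

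A second set-up assumed baseline mean 3500 and SD 1800, SD of change 1582, 2000 or 3000 steps per active hour, and adherence mean 0.5 with SD 0.15 or 0.30. It gave +1160 to +3510, with p<0.05 in every run.

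**4. When the instruction is not followed.** From the +735 scenario (percentage = positive and significant):

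| Departure | Slope | Percentage |
|---|---|---|
| Use at rest averaging 0.5 h/day | +512 | 100% |
| 1 h/day | +280 | 99.8% |
| 2 h/day | +94 | 73.5% |
| 4 h/day | +26 | 30.5% |
| Adherence falls with activity, logit shift 0.5 per SD | +517 | 99.5% |
| 1 per SD | +178 | 30.7% |
| 1.5 per SD | −144 | 0% |
| 2 per SD | −404 | 0% |

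The true oxygen effect is zero in every row.

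**5. Does the air arm repair it?** In the nine scenarios of step 3, the usage-by-arm interaction averaged −18 to +13 and was rejected in 4% to 13% of runs. It is not a clean control if adherence differs by arm. By the arithmetic of step 2, adherence of 0.5 on oxygen and 0.3 on air gives idealised slopes of 1500/0.5 = 3000 and 1500/0.3 = 5000, an oxygen-minus-air difference of −2000 with no oxygen effect. In the second set-up, with mean adherence 0.5 against 0.3 and SD 0.15, the interaction averaged −411 to −631 and was rejected in about 32% to 33% of runs. With 0.5 against 0.4 it was rejected in about 19% to 20%. A repeat of these cases gave 18% to 34%. With adherence SD 0.30, rejection stayed near 5%.

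**The case against.** The strongest reply is that this is one sentence on an analysis labelled exploratory and listed among the tertiary outcomes. Section 4.4 says such results supplement the primary analysis, and Appendix 1 proposes no table or figure for it. This stands and limits the severity. It does not remove the point: section 4.4 also says these analyses help to characterise the treatment effect, which is the reading that the association cannot bear.

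A second reply is that the simulated model is not the planned one. Read literally, usage as a random effect returns no average slope. In three example data sets with a random usage slope by site, the fit gave only a variance, although the mean predicted site slope was still about +600 to +640. That coding is a separate fault; correcting it alone would yield the slope discussed here. Nor does 4.12.4 exclude an arm term. But arm as a main effect still leaves one common slope, and the simulations included it.

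Third, LTOT starts are expected in only 5% (13 of 260), and sections 4.8 and 4.12.2 already report starts and reasons for stopping. So LTOT is a minor contributor.

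A reader might also infer that POC hours simply are walking time and that the slope must be positive. The documents support this only for participants who follow the instruction, and they give no data on use at rest or on adherence. The device log appears to cover months while steps cover 7 days, which would loosen the link further.

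**Conclusion.** The point holds as a minor one. Because section 2.3 ties use to movement in both arms, a positive usage-steps association is expected without any oxygen effect if the instruction is broadly followed. Use at rest weakens it and a strong inverse link between activity and adherence can reverse it. Whatever its sign, it does not estimate an impact of oxygen.

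Only N and the SD come from the SAP, so the slope sizes are illustrative. It is tempting to set them against 599 steps, but that figure is a difference between group means, whereas the slope is steps per POC hour and scales with an assumed conversion rate. It is equally tempting to treat the oxygen-minus-air difference in slopes as the effect of oxygen. It is more informative than a pooled slope, but usage is post-randomisation and step 5 of the working shows that the difference can be non-zero with no oxygen effect. No primary or secondary estimate depends on 4.12.4.

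**What to change.** In section 4.12.4:
- Replace *impact of* with *association between*.
- Fit usage, randomised arm and usage × arm as fixed effects, with baseline steps as a covariate.
- Report the usage slope with its confidence interval in each arm, taking the air-arm slope as the behavioural reference.
- Identify participants who started LTOT.
- State that the difference in slopes is more informative than a pooled slope but is not a causal estimate, because usage follows randomisation and adherence may differ by arm. The usage comparison already planned in 4.12.1 should be read alongside it.

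The cost is a few lines of SAP text and one interaction term, on data already collected. The downsides are that the interaction is estimated less precisely than a pooled slope and that the bias from differing adherence remains.
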